2.2 Sipuleucel-T (Provenge)

After decades of promise and research, sipuleucel-T (Provenge) has been the first vaccine therapy approved for treatment of any cancer in the United States. Sipuleucel-T involves *ex-vivo* sensitization of peripheral blood mononuclear cells to a custom prostatic acid phosphatase and granulocyte monocyte – colony stimulating factor (GM-CSF) fusion protein (PA 2024) followed by autologous transfusion. Sipuleucel-T is very well tolerated with mostly grade 2 side effects consistent with cytokine release. It has shown to improve survival by 3-4 months as compared to placebo in randomized, double blinded phase III clinical trials.(2, 3) Besides this modest improvement in survival, there has been no improvement in time to objective disease progression or an objective response rate (>25% decline in PSA).(2, 3) Although this has been a huge first stride in development of immunotherapies and first proof of principle, additional progress needs to be made before this technology has its fullest and most widely-applicable impact in treating cancers of prostate and other malignancies.

2.3 1-methyl-D-tryptophan (1-MT, indoximod)

Indoleamine 2,3-dioxygenase (IDO) is a key immune-modulatory enzyme that degrades tryptophan to bioactive kynurenine metabolites. The process and effects of tryptophan depletion and kynurenine metabolism together form the immuno-modulatory IDO pathway(4), which promotes peripheral immune tolerance by direct inhibition of effector T cells, activation of pre-existing Foxp3+ Tregs, and conversion of naïve T cells to Tregs. 1-MT is a competitive inhibitor of the immunoregulatory enzyme, IDO, a critical regulator of immunosuppressive responses.

In the preclinical studies, 1-MT was readily absorbed following oral administration in mice, rats, and dogs and the bio-availability ranged from 85 to 100%(6). It was determined to be safe in rats and pigs at doses as high as 3000 mg/m²/day (500 mg/kg/day) administered for 4 weeks and no significant clinical, hematology or chemistry abnormalities were noted.

In preclinical studies severity of toxoplasmosis was increased and activation of latent toxoplasmosis was noted in mice (unpublished data/7). Experimental colitis and encephalitis in preclinical studies were worsened by administration of 1-MT, although colitis and encephalitis have not been noted by administration of 1-MT alone. (8,9).

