We plan to offer trans-rectal biopsy of prostate prior to initiating therapy with sipuleucel-T and at 14 weeks from start of therapy for all patients who have an intact prostate and have not received radiation to the prostate. We will also offer biopsies to patients who have an easily accessible metastasis that can be biopsied before and after treatment. Biopsy of the primary tumor or metastatic site will help understand local immune response to treatment in individual patients. Simultaneous assessment of the immune response within the peripheral blood and within the tumor will help understand immune response to treatment and possibly establish markers of response. The information gained from this study would help devise strategies to better develop sipuleucel-T, indoximod and other immunotherapies for prostate cancer.

3 Patient Selection

Study entry is open to adult men regardless of race or ethnic background. While there will be every effort to seek out and include minority patients, the patient population is expected to be similar to that of other prostate cancer studies at the University Of Minnesota and other participating institutions.

Patients with metastatic castration resistant prostate cancer with minimally symptomatic or asymptomatic disease (the clinical indication for use of sipuleucel-t) will be considered for enrollment in this clinical trial.

Inclusion Criteria

- 3.1** Histologically documented adenocarcinoma of the prostate with metastatic disease as evidenced by soft tissue (e.g. lymphoid) and/or bony metastases on baseline CT scan of the abdomen and pelvis and/or bone scan
- 3.2** Castration-resistant based on a current or historical evidence of disease progression despite surgical or medical castration as demonstrated by one or more of the following:
 - PSA progression (defined as two consecutive PSA measurements at least 14 days apart ≥ 2.0 ng/ml and $\geq 50\%$ above the minimum PSA during castration therapy or above pre-treatment value if no response)
 - progression of measurable disease based on RECIST ($\geq 20\%$ increase in the sum of the diameters of all target lesions or the development of any new lesions – appendix III)
 - progression of non-measurable disease based on imaging studies pre section 9.4
- 3.3** Serum PSA ≥ 2.0 ng/ml at study enrollment
- 3.4** Castration levels of testosterone defined as ≤ 50 ng/dL at study enrollment

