11.2 Secondary Endpoints

- Antibodies to PA2024 as measured by ELISA
- Progression free survival
- Objective response rate as defined by Prostate Cancer Working Group -2 (PCWG2)(6)
- Overall survival and survival at two years
- Safety and tolerability
- Health related quality of life

12 Statistical Considerations

Our primary analysis will compare Tcell activation to PA2024 as measured by ELISPOT at 14 weeks between treatment groups using the two-sample t-test for unequal variance. This analysis will be completed on log-transformed data in the event that Tcell activation is skewed. A secondary analysis will be completed adjusting for any potential confounders or baseline differences using linear regression.(11)

Secondary endpoints CD54 count, antibodies to PA2024 and Tcell proliferation will be compared between groups in an unadjusted analysis using the two-sample t-test and an adjusted analysis using linear regression. Response rate will be summarized by group using contingency tables and the odds ratio for response will be estimated using logistic regression. Time to disease progression and overall survival will be summarized by Kaplan-Meier Curves and the hazard ratio estimated using Cox regression. In addition, quality of life will be measured by the FACT-P (a validated questionnaire consisting of four subscales of well-being: Physical, Social/Family, Emotional and Functional) and compared between treatment groups using the two-sample t-test for univariate analyses and multivariate linear regression for multivariate analysis.

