Appendix III – RECIST v 1.1

Response and progression will be evaluated in this study using the international criteria proposed by the revised Response Evaluation Criteria in Solid Tumors (RECIST) guideline (version 1.1) [*Eur J Ca* 45:228-247, 2009]. Changes in the largest diameter (unidimensional measurement) of the tumor lesions and the shortest diameter in the case of malignant lymph nodes are used in the RECIST criteria.

Disease Parameters

Measurable disease. Measurable lesions are defined as those that can be accurately measured in at least one dimension (longest diameter to be recorded) as ≥ 20 mm by chest x-ray, as ≥ 10 mm with CT scan, or ≥ 10 mm with calipers by clinical exam. All tumor measurements must be recorded in millimeters (or decimal fractions of centimeters).

Note: Tumor lesions that are situated in a previously irradiated area might or might not be considered measurable. *If the investigator thinks it appropriate to include them, the conditions under which such lesions should be considered must be defined in the protocol.*

Malignant lymph nodes. To be considered pathologically enlarged and measurable, a lymph node must be ≥ 15 mm in short axis when assessed by CT scan (CT scan slice thickness recommended to be no greater than 5 mm). At baseline and in follow-up, only the short axis will be measured and followed.

Non-measurable disease. All other lesions (or sites of disease), including small lesions (longest diameter < 10 mm or pathological lymph nodes with ≥ 10 to < 15 mm short axis), are considered non-measurable disease. Bone lesions, leptomeningeal disease, ascites, pleural/pericardial effusions, lymphangitis cutis/pulmonitis, inflammatory breast disease, and abdominal masses (not followed by CT or MRI), are considered as non-measurable.

Note: Cystic lesions that meet the criteria for radiographically defined simple cysts should not be considered as malignant lesions (neither measurable nor non-measurable) since they are, by definition, simple cysts.

'Cystic lesions' thought to represent cystic metastases can be considered as measurable lesions, if they meet the definition of measurability described above. However, if non-cystic lesions are present in the same patient, these are preferred for selection as target lesions.

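### The logistic-regression odds ratio planned for objective response has no sparse-data provision and may not be finite if response is about 5% or lower

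*Combined protocol and SAP*

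**What the plan says.** Objective response rate is a secondary objective (Section 1.2) and a secondary endpoint (Section 11.2). The whole analysis plan for it is one sentence in Section 12: response is tabulated by arm in contingency tables, and "the odds ratio for response will be estimated using logistic regression". No response-evaluable population is named, and nothing is said about sparse tables or exact methods. Section 12.1 sets the sample at 25 per arm on the ELISPOT endpoint; no response rate is assumed anywhere.

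On the definition, Section 11.2 lists "Objective response rate as defined by Prostate Cancer Working Group -2 (PCWG2)(6"), while Appendix III opens with "Response and progression will be evaluated in this study using the international criteria proposed by the revised Response Evaluation Criteria in Solid Tumors". Section 9 defines progression but not response.

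On who is counted, criterion 3.1 admits "soft tissue (e.g. lymphoid) and/or bony metastases on baseline CT scan of the abdomen and pelvis and/or bone scan", so men with bone disease only are eligible. Appendix III classes bone lesions as non-measurable, defines partial response on target lesions only, and gives non-measurable disease the categories CR, non-CR/non-PD, not evaluated and PD.

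**The concern.** There are two separate weaknesses.

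The first is the estimator. In a two-arm comparison of a binary outcome, the ordinary (maximum-likelihood) logistic odds ratio is finite only if both arms contain at least one responder and one non-responder. If one arm has no responders, the estimate runs to zero or infinity and the usual standard error and interval mean nothing. If neither arm has any, the odds ratio is undefined. With 25 men per arm and no stated fallback, the method would then be chosen after the counts were seen.

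The second is the reported rate. A man with bone-only disease can count as a responder under Appendix III only by complete response. If all randomised men form the denominator, the rate reflects the share with measurable disease as well as tumour shrinkage, and is hard to set beside other reports. The response definition itself is also not settled between Section 11.2 and Appendix III.

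**Working it through.** **1. The arm size.** Section 12.1 gives a coefficient of variation of 1.6, a 2.5-fold increase, a 0.05 level and 80% power. I assume a two-sided test, since sidedness is not stated. Log-scale SD = √ln(1 + 1.6²) = 1.127; difference = ln 2.5 = 0.916. With 25 per arm the noncentral t gives 80.4% power. The stated size reproduces, so n = 25 per arm is used below.

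**2. Chance that the odds ratio is not finite.** For a true rate p in both arms,

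P = 1 − [1 − (1 − p)^n − p^n]²

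The p^n term (every man responds) is negligible here. Example at p = 0.05: 0.95^25 = 0.277, so P = 1 − 0.723² = 0.478. All the rates are assumptions.

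| Assumed true rate, both arms | Expected responders of 50 | P(odds ratio not finite) |
|---|---|---|
| 2% | 1.0 | 84% |
| 5% | 2.5 | 48% |
| 10% | 5.0 | 14% |
| 15% | 7.5 | 3% |
| 20% | 10.0 | 0.8% |

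The chance falls below 10% once the rate exceeds about 11%. With unequal rates it is 63% at 2% vs 10%, and 29% at 5% vs 15%.

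**3. The same question by total responders.** With k responders among 50 men and no treatment effect, P(all in one arm) = 2·C(25,k)/C(50,k). This is 100% for k = 1, 49% for k = 2, 23% for k = 3, 11% for k = 4 and 5% for k = 5.

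**4. What failure looks like.** An ordinary logistic fit to 2/25 vs 0/25 did not converge. It stopped at a log odds ratio of 26.6 with a standard error of about 406,000. Fisher's exact test on the same table gives p = 0.49.

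**5. Does restricting to measurable disease help?** Suppose only men with measurable disease respond. The share measurable is an assumption, with arm sizes rounded.

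| Share measurable | Rate among measurable | All 25 per arm | Measurable only |
|---|---|---|---|
| 30% | 10% | 71.6% | 67.6% (8 per arm) |
| 50% | 10% | 47.8% | 48.5% (12 per arm) |
| 50% | 20% | 13.8% | 13.3% (12 per arm) |

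The chance of failure hardly moves, because the same responders are counted either way. What changes is the reported rate: 10% among measurable men becomes 0.5 × 10% = 5% among all.

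**6. Does case mix distort the comparison?** With 5% vs 15% among measurable men, the odds ratio is (0.15/0.85)/(0.05/0.95) = 3.35. With half the men bone-only and not responding, it is (0.075/0.925)/(0.025/0.975) = 3.16.

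**7. The citation.** Section 11.2 attaches reference 6 to PCWG2. Reference 6 is a study of tryptophan in infant formulas. The working-group recommendations are reference 10, which Section 9.2 cites correctly.

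**The case against.** The strongest objection is that nothing in the documents shows responders will be few. Section 2.2 says "there has been no improvement in time to objective disease progression or an objective response rate (>25% decline in PSA"), but that describes earlier sipuleucel-T trials against placebo. It reports no difference, gives no absolute rate, and does not concern sipuleucel-T followed by indoximod. At 15% or 20% the problem nearly vanishes. This stands: the size of the risk is conditional on an assumed rate.

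Section 12 also plans contingency tables, so counts and rates by arm will be reported even if the model fails. And it does not say maximum likelihood, so exact or Firth-penalised logistic regression would fit its wording. Both points stand and limit the harm. They do not remove the gap, since the sentence names no such method.

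Four stronger readings are tempting but not supported.

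- A reader might infer that bone-only men cannot respond. Appendix III lets non-measurable disease reach complete response; what is missing is partial response.
- A reader might infer that the comparison would reflect the bone-only mix rather than drug effect. Allocation is randomised 1:1, so the mix is balanced in expectation, and step 6 shows the odds ratio barely changes. Analysing all randomised men is legitimate.
- A reader might infer that restricting to measurable disease would rescue the odds ratio. Step 5 shows it does not.
- A reader might count the PSA gloss in Section 2.2 as a third definition of response for this study. It describes earlier results. The text to reconcile is Section 11.2 against Appendix III, and since PCWG2's response criteria are not reproduced, the documents do not show whether the two conflict in substance.

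**Conclusion.** The point holds in conditional form. With 25 per arm, an ordinary logistic odds ratio for response has roughly an even chance or worse of not being finite if the true rate is about 5% or lower in both arms. The chance is about 14% at 10% and about 1% at 20%. One might infer that the endpoint is likely to yield no usable estimate; without a response rate in the documents, that goes too far.

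The denominator issue is separate and concerns how the rate is described, not bias in the comparison. The wrong reference number in Section 11.2 is certain.

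The consequence is limited: this is a secondary endpoint with no stated power, and the sample size rests on ELISPOT. It is still worth changing, because the remedy costs little and removes a choice that would otherwise be made after the counts are known.

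**What to change.** **Section 12.** Keep the contingency tables. Make the between-arm comparison the difference in response proportions with an exact 95% CI, and test with Fisher's exact test. If an odds ratio is wanted, name exact or Firth-penalised logistic regression as the method.

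**Denominator.** State that the main rate uses all randomised men. Beside it, report soft-tissue response (CR or PR) among men with measurable disease at baseline.

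**Section 11.2 and Appendix III.** State how the PCWG2 definition and RECIST 1.1 fit together, correct the citation to reference 10, and report PSA decline as a separate outcome.

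**Cost.** No new patients or visits are needed: baseline, week 14 and week 28 imaging and serial PSA are already scheduled in Sections 6.1 and 6.2. The estimator change is wording only. Settling the response definition touches a listed endpoint, so it needs an amendment, made before unblinding. Exact intervals are somewhat wider, and the measurable-disease rate has a smaller denominator.

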1.2 Secondary Objectives

- To assess the safety of indoximod when administered post sipuleucel-T therapy
- To assess efficacy as measured by improvement in time to disease progression, objective response rate, overall survival
- To assess health related quality of life improvement on therapy

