6.1 Baseline and Post Treatment

Study	baseline	Weeks 0-28	Post rx visit	F/U
Evaluation	Prior to 1 st leukapheresis	Refer to table in 6.2	4 weeks after last dose of indoximod /placebo	Every 3 months from post-rx visit until 2 years from enrollment ⁸
Consent	X			
Medical history	X			
Physical exam	X			
Assessment of symptoms and analgesic needs	X		X	X
Weight	X		X	
Vital signs	X		X	
ECOG PS	X		X	
CBC/diff/plt, CD4 count	X		X	
Bun/creatinine, Na, K, Ca, Mg, tot. bili, AST, ALT, alkaline phosphatase, LDH, albumin, total protein	X		X	
Circulating Tumor Cells (CTCs)	X			
PT/INR, CPK	X			
Urinalysis ¹	X			
Testosterone	X		X	
HIV 1 & 2, hepatitis B, Hepatitis C, HTLV-1	X			
β-HCG	X			
ESR	X			
EKG	X			
CT of chest, abd, pelvis	X			X
Bone scan	X			X
PSA	X			X
Research Related				
FACT-P questionnaire	X		X	
TSH, Free T4, LH, FSH, ACTH, Cortisol ⁴	X			
Toxoplasma Ab titer	X		X ⁵	
Rheumatoid Factor	X			
C-Reactive Protein	X			
ANA panel ³ and auto-immune symptom checklist (app IV)	X			
C3, C4, CH50	X			
Samples for immune monitoring, K/T ratio and indoximod level (9 – 10 ml green tops, 1-10 ml red top)	X, X ⁶			
immune response biomarker (1-10 ml red top)	X			
Optional bx ⁷	X			

- 1- Proteinuria – any protein ≥ 2+ on dipstick or new urine active sediment/EOS should be evaluated per section 5.2.2
- 2- Toxoplasma serology positive patients will be offered prophylaxis with Septra DS per section 5.2.2
- 3- Refer to section 5.2.2 for positive ANA panel or symptoms of an autoimmune condition
- 4- Refer to section 5.2.2 for TSH > 5 or evidence of hypopituitarism
- 5- Retest sero-negative patients per section 5.2.2
- 6- Two separate sets of baseline samples to be done (i.e. at screening and prior to 1st sipuleucel-T infusion)
- 7- Biopsy for immune response biomarker only for those who provided additional consent within the treatment consent
- 8- Once disease progression is confirmed follow for survival status only

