6.2 During Treatment

Treatment	Week	Standard of Care			Research funded lab work to be performed by local (institutional) lab	Research Related Samples	indoximod / placebo count
Leukapheresis followed by sipuleucel-T infusion	0						
	1						
Leukapheresis followed by sipuleucel-T infusion	2						
	3						
Leukapheresis followed by sipuleucel-T infusion, start indoximod /placebo day after infusion	4	Prior to indoximod /placebo Physical exam, FACT-P				9 – 10 cc green, 1 – 10 cc red (pre indoximod/ placebo)	
indoximod /placebo twice daily continuously for 6 months	5						
	6	PE, review of side effects		CBC/diff/plt, chem ¹ , U/A ²	Thyroid function, C-reactive protein, ANA panel, Auto-immune symptom list	9 – 10 cc green, 1 – 10 cc red	Reconcile Drug
	7						
	8	PE, review of side effects, FACT-P	PSA	CBC/diff/plt, chem ¹ , U/A ²	Thyroid function, C-reactive protein, ANA panel, Auto-immune symptom list		Reconcile Drug
	9						
	10	PE, review of side effects		CBC/diff/plt, chem ¹ , U/A ²	Thyroid function, C-reactive protein, ANA panel, Auto-immune symptom list	9 – 10 cc green, 1 – 10 cc red	Reconcile Drug
	11-13						
	14	PE, review of side effects, FACT-P	PSA, CT of chest, abd, pelvis, bone scan	CBC/diff/plt, chem ¹ , CTCs ³ , U/A ²	Thyroid function, C-reactive protein, ANA panel, Auto-immune symptom list	9 – 10 cc green, 2 – 10 cc red, opt biopsy	Reconcile Drug
	15-19						
	20	PE, review of side effects, FACT-P	PSA	CBC/diff/plt, chem ¹ , U/A ²	Thyroid function, C-reactive protein, ANA panel, Auto-immune symptom list		Reconcile Drug
	21-23						
	24	PE, review of side effects		CBC/diff/plt, chem ¹ , protein, U/A ²			Reconcile Drug
	25-27						
28	PE, review of side effects, FACT-P	PSA, CT of chest, abd, pelvis, bone scan,	CBC/diff/plt, chem ¹ , U/A ²	Thyroid function, C-reactive protein, ANA panel, Auto-immune symptom list	9 – 10 cc green, 1 – 10 cc red	Final Reconcile Drug	

1- chem to include Bun/creatinine, Na, K, Ca, Mg, tot. bili, AST, ALT, alkaline phosphatase, LDH, albumin, total protein

2- Proteinuria – any protein ≥ 2+ on dipstick or new urine active sediment/EOS should be evaluated per section 5.2.2

3- CTCs - circulating tumor cells

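### The FACT-P comparison names no visit, baseline term or method for repeated scores, although two pre-drug and five later scores are collected

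*Combined protocol and SAP*

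**What the plan says.** The secondary objective in section 1.2 is "To assess health related quality of life improvement on therapy". Section 11.2 lists the endpoint only as "Health related quality of life".

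The analysis is one sentence in section 12. FACT-P is to be "compared between treatment groups using the two-sample t-test for univariate analyses" "and multivariate linear regression for multivariate analysis". The sentence does not name a visit, a change score, covariates, a way to combine repeated scores or a rule for missing scores. For the primary endpoint the same section fixes 14 weeks and says that the regression adjusts for confounders or baseline differences.

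The FACT-P schedule is spread over two tables:

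- Section 6.1, row "FACT-P questionnaire": marked at enrolment baseline and at the post-treatment visit, which is "4 weeks after last dose of indoximod /placebo". It is not marked in the follow-up column.
- Section 6.2, week 4: "Prior to indoximod /placebo Physical exam, FACT-P".
- Section 6.2, weeks 8, 14, 20 and 28: "PE, review of side effects, FACT-P". It is not listed at weeks 6, 10 or 24.

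That makes two scores before study drug, four on study drug and one after it.

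**The concern.** Improvement is judged against a starting point, and the trial collects two. The t-test, as written, uses neither. The regression could use one, but the plan does not say so. In a trial of about 25 men per arm, a patient's own earlier score is likely to be the strongest available predictor of his later one, so leaving it out would cost precision.

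The open visit is a separate matter. An analyst could test week 8, 14, 20 or 28, or the post-treatment visit, and comply with the plan each time. A nominally significant result at one visit would then be hard to interpret.

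The schedule also makes late scores selective. The section 6.2 table covers treatment, section 5.4 ends study drug at progression or toxicity, and follow-up contains no FACT-P. A man who stops early has a post-treatment questionnaire, but no later on-schedule score is planned for him. A t-test at a late visit would leave such men out, whereas a longitudinal model would use the scores they gave before stopping.

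**Working it through.** **The plan's own power figure.** Section 12.1 gives one power figure for a treatment comparison, and it is for ELISPOT: 25 per group, 2.5-fold increase, coefficient of variation 1.6, 0.05 level, 80% power.

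- Log-scale SD = √ln(1 + 1.6²) = 1.127; difference = ln 2.5 = 0.916; standardised effect = 0.916/1.127 = 0.813.
- Noncentral t, 48 df, two-sided 0.05: power 80.4%. The stated figure reproduces.

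No such figure is given for quality of life. By the same method, a t-test on a single FACT-P score with 25 per arm needs a true difference of 0.81 SD for 80% power.

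**Effect of the pre-drug score.** The documents give no FACT-P SD, target difference or pre–post correlation r. I assume a true difference of 0.5 SD, equal SDs before and after, and r from 0.3 to 0.7. Variances are relative to a raw score.

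- Raw-score t-test: variance 1, effect 0.5.
- Change-score t-test: variance 2(1 − r), effect 0.5/√[2(1 − r)].
- Covariate adjustment: variance 1 − r², effect 0.5/√(1 − r²), 47 df.
- Noncentrality = effect × √(25/2), two-sided 0.05.

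| r | Raw t-test: power | Change score: variance, power | Adjusted: variance, power |
|---|---|---|---|
| 0.3 | 41% | 1.40, 31% | 0.91, 44% |
| 0.5 | 41% | 1.00, 41% | 0.75, 52% |
| 0.6 | 41% | 0.80, 49% | 0.64, 58% |
| 0.7 | 41% | 0.60, 61% | 0.51, 68% |

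For r = 0.5 to 0.7, adjustment gains 11 to 27 percentage points over the raw score and about 11 down to 7 over the change score. The difference detectable with 80% power falls from 0.81 SD (raw) to 0.70 SD at r = 0.5 and 0.58 SD at r = 0.7.

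These are single-visit figures. With complete data, a repeated-measures model gives about the same precision as covariate adjustment for its week-14 contrast. The power gain comes from the covariate; the longitudinal part helps when scores are missing.

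**Open visit.** Suppose each visit is tested at 0.05, there is no effect, and the test statistics are equally correlated normals (correlation assumed). The chance that at least one |z| exceeds 1.96 is:

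| Visits tested | Correlation 0.5 | Correlation 0.8 | Independent |
|---|---|---|---|
| Weeks 8, 14, 20, 28 | 15.6% | 11.4% | 1 − 0.95⁴ = 18.5% |
| The same plus post-treatment | 18% | 13% | 1 − 0.95⁵ = 22.6% |

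**The case against.** **The regression.** Quality of life has two planned analyses, so a reader who infers that it rests on a t-test alone is wrong. The primary endpoint's regression in the same section adjusts for baseline differences, and a similar reading for FACT-P is natural. If the regression carries a pre-drug score, the power gain over it is nil. This stands as far as it goes: the documents do not show that the pre-drug score is discarded. They also do not say that it is used, which score it would be, or at which visit.

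**Raw scores are an inference.** Section 12 does not say what enters the t-test, and an objective about improvement fits change from baseline equally well. This stands. The fair comparator is therefore a range of 41% to 61%, not 41% alone.

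**No passage plans to test every visit and report the best.** This also stands. The false-positive figures show what the wording permits, not what is planned. The post-treatment visit falls after the last dose, so the four on-drug visits are the better count for an objective about therapy.

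**Missing scores.** No dropout rate is given. Section 5.4 intends at least 12 weeks of study drug before progression is declared, that is, to about week 16 (4 + 12), so progression should remove few men before week 14. The concern has more force at weeks 20 and 28.

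**Choice of baseline.** FACT-P asks about the past 7 days, and week 4 includes the third leukapheresis and infusion, so that score may carry procedure effects. This is a reason to state and justify the choice, not to leave it open.

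**Importance.** This is a secondary endpoint without a power claim. Nothing here touches the primary result.

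**Conclusion.** The point holds as a gap in specification for which a better method is available at no extra data cost. The t-test as written has no baseline term, the regression has no named covariates, no FACT-P visit is fixed, and no method for repeated scores is given.

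At 25 per arm and an assumed 0.5 SD effect, baseline adjustment gives 52% to 68% power (r = 0.5 to 0.7, assumed), against 41% raw or 41% to 61% on change scores. If all four on-drug visits were tested, the chance of at least one false positive would be about 16% to 11% (between-visit correlation 0.5 to 0.8, assumed).

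Twenty-five per arm is probably an upper limit. The synopsis speaks of about 50 men enrolled, enrolment precedes randomisation, and section 4.3 removes men who are not randomised.

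A reader might infer that the trial is too small for its quality-of-life claim. The documents make no such claim, so the sample size is not in question.

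**What to change.** Rewrite the quality-of-life sentence in section 12 to state:

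- **Score:** FACT-P total. Section 12 describes four well-being subscales, whereas Appendix V also has an additional-concerns block, so the score needs naming.
- **Main analysis:** a repeated-measures model with treatment, visit and their interaction over weeks 8, 14, 20 and 28, including every randomised man with at least one of these scores. State the missing-at-random assumption that it makes.
- **Covariate:** a named pre-drug FACT-P score. Week 4 is the last before study drug; the enrolment score can be added.
- **Contrast:** the week-14 treatment difference with its confidence interval, as the single stated comparison. It matches the time of the primary endpoint. Other visits are descriptive.
- **Post-treatment visit:** reported separately, because its study week depends on the date of the last dose.

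The t-test can remain as a supportive analysis at week 14. The cost is a few sentences in the plan and slightly more analysis work, with no new visits, questionnaires or patients.
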